## 18.1.6. HFS Child Questionnaire

Study ID: \_\_\_\_\_

Subject ID: \_\_\_\_\_

Today's Date: \_\_\_\_\_

Study ID # \_\_\_\_\_

University of Virginia

### Child/Teen Low Blood Sugar Survey

We want to find out more about what low blood sugar makes young people feel and do. Please answer the questions below as honestly as you can.

I. Below is a list of things young people with diabetes sometimes DO TO KEEP FROM HAVING LOW BLOOD SUGAR. Circle the number that best describes YOU.

0=NEVER 1=RARELY 2=SOMETIMES 3=OFTEN 4=ALMOST ALWAYS

- |     |   |   |   |   |   |   |
|-----|---|---|---|---|---|---|
| 1.  | Eat large snacks at bedtime                                       | 0 | 1 | 2 | 3 | 4 |
| 2.  | Try not to be by myself when my sugar is likely to be low         | 0 | 1 | 2 | 3 | 4 |
| 3.  | Keep blood sugars a little high to be on the safe side            | 0 | 1 | 2 | 3 | 4 |
| 4.  | Keep blood sugar higher when I will be alone for awhile           | 0 | 1 | 2 | 3 | 4 |
| 5.  | Eat something as soon as I feel the first sign of low blood sugar | 0 | 1 | 2 | 3 | 4 |
| 6.  | Take less insulin when I think my blood sugar might get too low   | 0 | 1 | 2 | 3 | 4 |
| 7.  | Keep my blood sugar higher when I am going to be away from home   | 0 | 1 | 2 | 3 | 4 |
| 8.  | Carry some kind of sugar, drink, or food with me                  | 0 | 1 | 2 | 3 | 4 |
| 9.  | Try not to do a lot of exercise when I think my sugar is low      | 0 | 1 | 2 | 3 | 4 |
| 10. | Check my blood sugar often when I go away from home               | 0 | 1 | 2 | 3 | 4 |

II. Below is a list of things that young people with diabetes sometimes worry about concerning low blood sugars. Circle the number that best describes YOU.

0=NEVER 1=RARELY 2=SOMETIMES 3=OFTEN 4=ALMOST ALWAYS

- |     |   |   |   |   |   |   |
|-----|---|---|---|---|---|---|
| 11. | Not recognizing that my blood sugar is low                            | 0 | 1 | 2 | 3 | 4 |
| 12. | Not having food, fruit, or juice with me when my blood sugar gets low | 0 | 1 | 2 | 3 | 4 |

Study ID: \_\_\_\_\_

Subject ID: \_\_\_\_\_

Today's Date: \_\_\_\_\_

Study ID # \_\_\_\_\_

University of Virginia

Child/Teen Low Blood Sugar Survey

We want to find out more about what low blood sugar makes young people feel and do. Please answer the questions below as honestly as you can.

I. Below is a list of things young people with diabetes sometimes DO TO KEEP FROM HAVING LOW BLOOD SUGAR. Circle the number that best describes YOU.

0=NEVER 1=RARELY 2=SOMETIMES 3=OFTEN 4=ALMOST ALWAYS

- |     |   |   |   |   |   |   |
|-----|---|---|---|---|---|---|
| 1.  | Eat large snacks at bedtime                                       | 0 | 1 | 2 | 3 | 4 |
| 2.  | Try not to be by myself when my sugar is likely to be low         | 0 | 1 | 2 | 3 | 4 |
| 3.  | Keep blood sugars a little high to be on the safe side            | 0 | 1 | 2 | 3 | 4 |
| 4.  | Keep blood sugar higher when I will be alone for awhile           | 0 | 1 | 2 | 3 | 4 |
| 5.  | Eat something as soon as I feel the first sign of low blood sugar | 0 | 1 | 2 | 3 | 4 |
| 6.  | Take less insulin when I think my blood sugar might get too low   | 0 | 1 | 2 | 3 | 4 |
| 7.  | Keep my blood sugar higher when I am going to be away from home   | 0 | 1 | 2 | 3 | 4 |
| 8.  | Carry some kind of sugar, drink, or food with me                  | 0 | 1 | 2 | 3 | 4 |
| 9.  | Try not to do a lot of exercise when I think my sugar is low      | 0 | 1 | 2 | 3 | 4 |
| 10. | Check my blood sugar often when I go away from home               | 0 | 1 | 2 | 3 | 4 |

II. Below is a list of things that young people with diabetes sometimes worry about concerning low blood sugars. Circle the number that best describes YOU.

0=NEVER 1=RARELY 2=SOMETIMES 3=OFTEN 4=ALMOST ALWAYS

- |     |   |   |   |   |   |   |
|-----|---|---|---|---|---|---|
| 11. | Not recognizing that my blood sugar is low                            | 0 | 1 | 2 | 3 | 4 |
| 12. | Not having food, fruit, or juice with me when my blood sugar gets low | 0 | 1 | 2 | 3 | 4 |

Study ID:

Subject ID:

13.	Feeling dizzy or passing out in public because of low blood sugar	0	1	2	3	4
14.	Having a low blood sugar while asleep	0	1	2	3	4
15.	Embarrassing myself because of low blood sugar	0	1	2	3	4
16.	Having low blood sugar while I am by myself	0	1	2	3	4
17.	Looking "stupid" or clumsy in front of other people	0	1	2	3	4
18.	Losing control because of low blood sugar	0	1	2	3	4
19.	No one being around to help me during a low	0	1	2	3	4
20.	Making a mistake or having an accident at school	0	1	2	3	4
21.	Getting in trouble at school because of something that happens when my sugar is low	0	1	2	3	4
22.	Having seizures	0	1	2	3	4
23.	Getting long term complications from low blood sugar	0	1	2	3	4
24.	Feeling dizzy or woozy when my blood sugar is low	0	1	2	3	4
25.	Having a low blood sugar	0	1	2	3	4

---

## 18.2. Sensor Dislodgement / Suspected Occlusion Diary

	PROTOCOL ID	STUDY			SUBJECT IDENTIFICATION SITE			SUBJECT			
	CEP 266	2	6	6	-				-		

### Sensor Dislodgement / Suspected Occlusion (w/o Occlusion Alarm)

#### Subject Log

Please record date when your sensor becomes dislodged or when you suspect that an occlusion of your infusion set has occurred. Select a reason for it from the "How did it happen?" drop-down list. If the reason is not listed there, please explain in the adjacent "Comment" field.

Date	What happened?	How did it happen?	Comment (if reason is "Other")
Click here to enter a date.	Choose an item.	Choose an item.	Choices: 1. Bumped sensor against object. 2. Came off during clothing change 3. Came off during exercise 4. Came off during sleep 5. Cannot tell how it happened 6. When infusion set was inserted 7. Other
Click here to enter a date.	Choose an item.	Choose an item.	
Click here to enter a date.	Choose an item.	Choose an item.	
Click here to enter a date.	Choose an item.	Choose an item.	
Click here to enter a date.	Choose an item.	Choose an item.	
Click here to enter a date.	Choose an item.	Choices: 1. Complete Sensor Dislodgement 2. Partial sensor dislodgement with sensor remaining in skin 3. Suspected Occlusion without occlusion alarm	
Click here to enter a date.	Choose an item.		
Click here to enter a date.	Choose an item.		
Click here to enter a date.	Choose an item.		
Click here to enter a date.	Choose an item.	Choose an item.	
Click here to enter a date.	Choose an item.	Choose an item.	
Click here to enter a date.	Choose an item.	Choose an item.	
Click here to enter a date.	Choose an item.	Choose an item.	

Version	Version Date
Draft	29 Jul 2013

Abbreviation	Definition
A1C	Glycosylated hemoglobin
AE	Adverse Event
MDR	Medical Device Reporting
SAE	Serious Adverse Event
UADE	Unanticipated Adverse Device Effect

3 Introduction

The approval of the MiniMed® 530G Pump model (MMT-751, MMT-551) occurred on 27th September 2013. Prior to submitting the IDE for a device that incorporates the Threshold Suspend (TS) feature in the United States, Medtronic evaluated and released the Medtronic MiniMed® Paradigm Veo pump in Europe and other part of the world. One of the first steps towards approval of a similar device in the United States was taken with the CEP 235 study. The study was completed in 2011 and the study report has been submitted.

This Statistical Analysis Plan (SAP) was created using CEP266, Protocol version E. Please refer to the Reference section for other documents used to create this SAP.

This SAP dictates the contents in the final study report only.

4 Study Objectives

The purpose of the study is to provide ongoing surveillance of the TS feature with a sensor augmented pump system over a 12-month period.

The study objective is to demonstrate that home use of Threshold Suspend (TS) is not associated with glycemic deterioration. This objective will be demonstrated in several ways using two sub-studies:

- 1) Sub-study 1: Multi-Center Trial

- Comparison of A1C measurement from baseline to end of study in the CEP266 study population
- 2) Sub-study 2: Commercial Data Evaluation
 - CareLink® data from the commercial MiniMed 530G users
 - Summary of supplementary data on hospitalized patients using the 530G system; taken from Medical Device Reporting (MDR)
 - Review of published data on the TS feature
 - Review of unpublished data on the TS feature, as available

5 Investigation Plan

5.1 Study Design

The evaluation of Threshold Suspend(TS) feature is conducted by two sub-studies: 1) Commercial Data Evaluation; 2) Prospective Multi-Center Trial.

5.1.1 Multi-Center Trial

The Multi-center trial was initiated to observe the Threshold Suspend (TS) feature with a sensor-augmented insulin pump (Medtronic MiniMed® 530G insulin pump) in patients 16 and older with insulin requiring diabetes over a period of one year.

In addition, additional data from commercial use will be analyzed/summarized to support the Multi-center trial as the enrolled population is lower (N=426) than the anticipated N=1000 subjects.

5.1.2 Commercial Data Evaluation

Additional dataset:

- CareLink® data from the commercial MiniMed 530G users
- Summary of supplementary data on hospitalized patients using the 530G system; taken from Medical Device Reporting (MDR)
- Review of published data on the TS feature
- Review of unpublished data on the TS feature, as available

5.2 Study Population of Multi-Center Trial

A total of 426 subjects have been enrolled in the study.

40 Investigational centers were activated across the United States. Selection was based on Investigator's experience and qualifications, availability of sufficient resources to carry out the required study procedures and the investigator's ability to recruit subjects into the study.

5.3 Inclusion Criteria

1. Subject is age 16 or older at time of screening
2. Subject has been diagnosed with diabetes mellitus for at least one year prior to screening.
3. Subject is currently on pump therapy.
4. Subject is transitioning to the 530G insulin pump system with the TS feature turned ON.
5. Subject is willing to complete all study related activities
6. Subject is willing to upload data every 21 days from the study pump

7. Subject must have Internet access and access to a computer system that meets the requirements for uploading the pumps. This may include use of family or friend's computer system with Internet access.
8. Subject is able (by insurance or financial means) to cover the initial investment and ongoing cost of the 530G insulin pump and consumables, CGM, CONTOUR NEXT LINK RF enabled meter and supplies for the length of the study- 1 year.

5.4 Exclusion Criteria

1. Subject is actively participating in an investigational study (drug or device) wherein he/she has received treatment from an investigational study drug or investigational study devices in the last 2 weeks.
2. Subject is a woman of child-bearing potential who has a positive pregnancy test at screening or plans to become pregnant during the course of the study
3. Subject is being treated for hyperthyroidism at time of screening
4. Subject has an abnormality ($>1.8\text{mg/dL}$) in creatinine at time of screening visit
5. Subject has an abnormality (out of reference range) in thyroid-stimulating hormone (TSH) at time of screening visit. If TSH is out of range, Free T3 and Free T4 will be tested. Subject may be included with TSH out of range as long as Free T3 and Free T4 are in normal reference range.
6. Subject has taken any oral, injectable, or IV steroids within 8 weeks from time of screening visit, or plans to take any oral, injectable, or IV steroids during the course of the study
7. Subject is currently abusing illicit drugs
8. Subject is currently abusing prescription drugs
9. Subject is currently abusing alcohol
10. Subject has sickle cell disease or hemoglobinopathy
11. Subject has received red blood cell transfusion or erythropoietin within 3 months prior to time of screening or plans to receive red blood cell transfusion or erythropoietin over the course of study participation
12. Subject diagnosed with current eating disorder such as anorexia or bulimia
Subject has been diagnosed with chronic kidney disease that results in chronic anemia

6 Determination of Sample Size

6.1 Sample Size for Primary Endpoint

The overall mean change in A1C from baseline to the end of study will be estimated and compared by a non-inferiority test with an A1C margin of 0.4% and a significance level of 0.025 (one-sided) with the CEP 266 study population. The null hypothesis will be rejected if the one-sided 97.5% upper confidence limit of the mean change in A1C is less than 0.4%

The hypothesis is mathematically expressed as:

Ho: $\mu \geq 0.4\%$

Ha: $\mu < 0.4\%$

Where 0.4% is the pre-specified non-inferiority margin, μ is the mean of change in A1C (%).

Assuming the mean of change in A1C from baseline to the 12-month follow-up visit is zero, the standard deviation of change in A1C is 1%, SAS power and sample size calculator shows that a total of 100 subjects will provide over 95% power to detect the non-inferiority with a margin of 0.4% and with one-sided type I error of 0.025.

6.2 Sample Size for Adverse Event

Based on previous STAR3 IDE study (G060159), the serious adverse event rate for DKA and severe hypoglycemia was 14.79% (1.27% for DKA and 13.52% for severe hypoglycemia). Assuming a one-year serious adverse event rate for DKA and severe hypoglycemia of 14.5%, a sample size of 480 would produce a one-sided 95% upper confidence limit around 17.5%. The actual one-sided 95% upper confidence limit for DKA incidence rate and severe hypoglycemia incidence rate will also be report separately.

7 Statistical Methods

7.1 Study Subjects

7.1.1 Disposition of Subjects

The number of subjects enrolled, completed the trial and those that discontinued early will be provided along with the reasons for early discontinuation. The number of subjects completing each scheduled visit overall will be provided in addition to stratification by protocol in which they were enrolled under.

An enrolled subject is one that has signed consent to be included in the study. A subject is deemed as a participating subject if they have completed the eligibility assessment and are not exited as a screen failure. Subjects will be categorized by demographic information for both the categories of Enrolled subjects and Participating subjects. See section 7.2.1.2 Descriptive Statistics.

7.1.2 Clinical Investigation Plan (CIP) Deviations

All protocol deviations will be presented.

7.1.3 Analysis Sets

7.1.3.1 Intention to Treat (ITT) Population

The Intention to Treat (ITT) population will include all enrolled subjects.

7.1.3.2 Completed Case (CC) Population

The Completed Cases (CC) population is all subjects who complete the trial.

7.1.3.3 Efficacy Population

The primary efficacy analysis will be performed on the CC population.

7.1.3.4 Safety Population

The Safety Population will be the ITT population (include all enrolled subjects).

7.2 General Methodology

7.2.1 Primary Efficacy Analysis

A mixed effects model will be used to produce the estimate and confidence interval of the overall mean change in A1C while accounting for inter-site variability: The 97.5% upper confidence interval of A1C will be calculated and compared to the 0.4% non-inferiority margin with the CEP 266 study population. As for endpoint analysis, the proposed mixed effects model using all A1C measurements has more power than the model only using Change in A1C from baseline to one-year visit.

$$Y_{ij} = X_{ij}\beta + B_i + B_{ij} + \varepsilon_{ij}$$

where

$Y_{ij} = (Y_{ij1}, \dots, Y_{ij5})'$ is the A1C measurement vector for the jth subject in the ith site;

$$X_{ij} = \begin{pmatrix} 1 & 0 & 0 & 0 & 0 \\ 1 & 1 & 0 & 0 & 0 \\ 1 & 0 & 1 & 0 & 0 \\ 1 & 0 & 0 & 1 & 0 \\ 1 & 0 & 0 & 0 & 1 \end{pmatrix}$$

is a the covariate vector for the jth subject in the ith site;

$$\beta = \begin{pmatrix} \beta_0 \\ \beta_1 \\ \beta_2 \\ \beta_3 \\ \beta_4 \end{pmatrix}$$

is the coefficient vector, β_0 estimate the mean A1C at baseline, β_4 estimate the mean change of A1C from baseline to one-year visit;

$B_i = (b_{i1}, \dots, b_{i5})'$ is the random effect vector for the ith site;

$B_{ij} = (b_{ij1}, \dots, b_{ij5})'$ is the random effect vector for the jth subject in the ith site;

$\varepsilon_{ij} = (\varepsilon_{ij1}, \dots, \varepsilon_{ij5})'$ is the random error term;

“The mean of baseline A1C measurement is estimated by β_0 , mean of 3-month A1C measurement estimated by $\beta_0 + \beta_1$, ..., mean of 12-month A1C measurement estimated by $\beta_0 + \beta_4$, i.e., β_4 estimate the mean change of A1C from baseline to one-year visit; the 97.5% upper confidence interval of β_4 will be calculated and compared the 0.4% non-inferiority margin.”

7.2.1.1 Sensitivity Analysis

Sensitivity analysis will be performed on the ITT population with multiple imputations. The missing data in A1C measurements will be handled by the multiple imputation approach using imputation regression

method, where the independent variables in the regression model are age, gender, baseline A1C and BMI. In each imputed dataset, the missing A1C data will be imputed by $\hat{y} + z\hat{\sigma}$, where \hat{y} is the predicted value from regression, Z is a standard normal random variable, $\hat{\sigma}$ is the estimated standard deviation of the random residual from the regression model. The imputation will be performed five times using the MI procedure and the analysis results will be combined to form one inference using the MIANALYZE procedure in SAS 9.3.

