## 11.9. Subject Withdrawal, Screen Failures and Data Censure

Subjects may choose to withdraw from the study at any time by notifying Investigational Center staff of their intent.

If a subject chooses to end his or her study participation or if a subject is removed from the study at the Investigator's discretion, the reason for termination must be documented both in source documents and on the appropriate eCRF.

Subjects may also be withdrawn from the study at the discretion of the Investigator. A subject will be withdrawn from the study by the investigator if:

- In the opinion of the Investigator, the subject's health or safety would be compromised by continuing in the study
- In the opinion of the Investigator, it is in the subject's best interest to discontinue participation in the study

A subject's data may be subject to censure if any of the following occurs:

- During the course of the study, subject begins participation in another investigational study (drug or device).
- During the course of the study, subject begins abusing illicit drugs.
- During the course of the study subject begins abusing prescription drugs.
- During the course of the study subject begins abusing alcohol.

Documentation of the reason(s) leading to subject withdrawal will be kept in the subject's source file.

Should a subject fail to meet inclusion/exclusion criteria, their study participation will end and the subject will exit the study as a screen failure. The criterion not met should be documented.

Subjects may be rescreened after a minimum of three months if they do not meet inclusion/exclusion criteria at the time of their original screening. Rescreening may occur up to two times.

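### No planned analysis varies the assumption that subjects who leave the multi-center trial change in A1C like those observed, so the plan cannot show how far the non-inferiority conclusion depends on it

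*SAP*

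**What the plan says.** SAP 7.1.3.3 states "The primary efficacy analysis will be performed on the CC population", meaning subjects who complete the trial; Protocol 7.1.2.3 agrees. The model in SAP 7.2.1 is a mixed model on A1C at baseline and the four follow-up visits. The test compares the 97.5% upper limit of the 12-month change with 0.4%.

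SAP 7.2.1.1 and Protocol 7.1.3.2 add one sensitivity analysis: "Sensitivity analysis will be performed on the ITT population with multiple imputations". The listed predictors are age, gender, baseline A1C and BMI. The 3-, 6- and 9-month A1C values are not among them, nor is the reason for leaving, and no shift is applied to leavers. SAP 7.4 describes the same imputation but calls it the primary analysis, which contradicts SAP 7.1.3.3.

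Protocol 11.9 lets subjects leave at any time and has the investigator withdraw a subject on grounds that include "In the opinion of the Investigator, the subject's health or safety would be compromised by continuing in the study". The plan also reports numbers of and reasons for early discontinuation (SAP 7.1.1), A1C change at each visit by baseline A1C cohort (SAP 7.2.3), and severe hyperglycemia and DKA in all enrolled subjects (SAP 7.2.2).

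**The concern.** Whichever population is primary, the plan holds two A1C analyses with essentially one assumption about leavers. The completer analysis takes them to change like completers. The imputation takes them to change like observed subjects with the same four baseline characteristics. Restricting the mixed model to completers also discards the interim A1C of those who left, and the imputation as specified does not use those values either.

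A health-related withdrawal rule makes it plausible that leavers differ. If their A1C is worse, dropping them or imputing them as average lowers the estimated change and its upper limit. In a single-group non-inferiority test that favours passing. The two analyses would then agree because they share the error, and the agreement could be read as robustness. This is the multi-center trial's only hypothesis test; the commercial data evaluation has its own.

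**Working it through.** **Inputs from the documents.** SAP 6.1 gives "a significance level of 0.025 (one-sided) with the CEP 266 study population"; "Where 0.4% is the pre-specified non-inferiority margin"; "Assuming the mean of change in A1C from baseline to the 12-month follow-up visit is zero"; and "the standard deviation of change in A1C is 1"%. SAP 5.2 gives 426 enrolled. SAP 7.1.1 defines enrolled as having signed consent, so 426 includes screen failures and is an upper bound.

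**Inputs assumed, because the documents give none.** Dropout d from 10% to 30%. Excess 12-month A1C change of leavers over completers, delta, from 0 to 1.0 points.

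**The plan's own figure.** SAP 6.1 says "a total of 100 subjects will provide over 95% power to detect the non-inferiority with a margin of 0.4"%. Normal approximation: Phi(0.4 × √100 / 1 − 1.96) = Phi(2.04) = 97.9%. Noncentral t: 97.7%. The figure reproduces.

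**False-pass rate of the completer analysis.** Set the true mean change over all subjects at the margin, 0.4%. Completers then average 0.4 − d × delta, with n = 426 × (1 − d). Treating the 12-month change as a one-sample mean:

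P(pass) = Phi(d × delta × √n / 1 − 1.96)

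For d = 20% and delta = 0.5: n = 341, √n = 18.47, and Phi(0.10 × 18.47 − 1.96) = Phi(−0.113) = 45.5%.

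| Dropout (n) | delta 0 | delta 0.25 | delta 0.5 | delta 1.0 |
|---|---|---|---|---|
| 10% (383) | 2.5% | 7.1% | 16.3% | 49.9% |
| 20% (341) | 2.5% | 15.0% | 45.5% | 95.8% |
| 30% (298) | 2.5% | 25.3% | 73.5% | 99.9% |

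**The planned imputation, by simulation.** There were 2,000 trials per setting, with regression imputation on the four listed predictors, five imputations and Rubin's rules. The assumed baseline A1C SD was 1.2%. Regression parameters were redrawn for each imputation.

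- delta 0: passes 2.6% at 10% dropout and 2.5% at 20%.
- delta 0.5: passes 16.3%, 43.3% and 67.6% at 10%, 20% and 30% dropout.
- The average mean change at delta 0.5 was 0.350, 0.300 and 0.251 for completers, against 0.349, 0.299 and 0.250 for the imputation. They differ by 0.001, so comparing the two would not reveal the bias.

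**Using interim A1C.** In the same simulation every leaver already showed the rise at month 6. Adding that value to the imputation model cut the pass rate at 20% dropout and delta 0.5 from 43.3% to 15.2%. That is an improvement, but not a return to 2.5%.

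**Shift that flips a pass.** Hold the standard error at its completer value and solve for the shift in leavers that brings the upper limit to 0.4. At 25% missing, SE = 1/√(426 × 0.75) = 0.0559 and 1.96 × SE = 0.110.

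- Observed mean 0: (0.4 − 0 − 0.110)/0.25 = 1.16 points.
- Observed mean 0.1: (0.4 − 0.1 − 0.110)/0.25 = 0.76 points.
- Observed mean 0.2: (0.4 − 0.2 − 0.110)/0.25 = 0.36 points.

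**Shift that brings the true mean itself to 0.4.** This is (0.4 − completers' mean)/d. At 20% dropout it is 2.0, 1.0 and 0.5 points for completers' means of 0, 0.2 and 0.3.

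**The case against.** The strongest reply is that the size rests on inputs the documents do not contain and on a true mean placed exactly at the margin. That stands. The bias itself is d × delta. At 20% dropout and delta 0.5 it is 0.10 points, as if completers were tested against a margin of 0.50. If completers show the zero change that SAP 6.1 assumes, only a large excess in leavers would overturn the result.

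A reader might infer from Protocol 11.9 that leavers must have worse A1C. The documents do not support this. The clause is a general safety rule that does not mention A1C. It could equally cover hypoglycemia or unrelated illness, and subjects may leave for their own reasons. Protocol 11.8 names change in insurance or financial status as a barrier to adherence. The direction is open.

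A reader might also infer that nothing in the plan would expose the problem. That is too strong: discontinuation reasons, visit-wise A1C and adverse events could raise suspicion. None of them measures the effect on the test.

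Finally, 426 overstates the number at risk. Screen failures have no follow-up, and those who fail on screening laboratory tests need not attend Visit 1, where baseline A1C is first drawn. With fewer participating subjects the inflated rates would be somewhat lower.

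**Conclusion.** The point holds as a gap in the sensitivity analysis, not as a demonstrated bias. Both A1C analyses make effectively the same assumption about leavers, and no planned analysis tests or quantifies a departure from it. If leavers do not differ, the false-pass rate is about 2.5% as intended. If they are 0.5 points worse and the true rise is 0.4%, it is roughly 16% to 74% across 10% to 30% dropout for completers, and 16% to 68% for the imputation. Those figures rest on the assumed dropout and difference, SD 1%, and 426 as an upper bound. They should not be read as the trial's actual error rate. The practical risk is mainly where completers rise by about 0.2% to 0.3%; a tipping value would tell the reader whether that case applies. This is a cheap improvement.

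**What to change.** In SAP 7.2.1.1 and Protocol 7.1.3.2:

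1. Add the 3-, 6- and 9-month A1C values to the imputation model.
2. Add a delta-adjusted version of that imputation. Raise the imputed 12-month A1C by 0 to 2.0 points in steps of 0.1 for participating subjects who left before Visit 5, not for screen failures. Report the smallest shift at which the 97.5% upper limit reaches 0.4% beside the non-inferiority conclusion.
3. Reconcile SAP 7.1.3.3 with SAP 7.4, so that it is clear which result the tipping value qualifies.

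No new data are needed. The cost is a little more programming and one table. The downside is that a small tipping value would oblige the sponsor to word the conclusion less firmly.
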